7.3.3. Bristol Stool Chart

The form of faeces will be assessed by clinical staff using the Bristol Stool Chart when collecting faecal samples for faecal occult blood test in treatment periods (see Schedule of Assessments in [Appendix 6](#)). The form of faeces may also be assessed at other times if judged to be clinically appropriate.

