3.7. Dose Escalation Stopping Criteria

The study will be halted if 1 or more subjects experience an SAE that is considered to be related to IMP or 2 or more subjects in the same group experience severe AEs that are

considered to be related to IMP. If, following an internal safety review, the Sponsor deems it appropriate to restart the study, this can be done following approval of a substantial protocol amendment.

For both Parts A and B, a consultation between the Investigator, Sponsor, and Labcorp Drug Development Medical Monitor will be held prior to dosing the next group. Dose escalation will stop if:

- Clinically relevant signs or symptoms of similar nature occur in 2 or more subjects in a group that, in the opinion of the Investigator, warrant stopping of dose escalation. In particular, the Investigator (or designee) should carefully monitor signs or symptoms below:
 - symptoms such as inappetence, abdominal distension, abdominal discomfort, abdominal pain, nausea and vomiting
 - signs/findings such as abdominal tenderness and decreased or absent peristaltic sounds
 - abnormal faeces such as diarrhea, hematochezia, and melena.
- Inappetence, abdominal distension, abdominal discomfort, abdominal pain, nausea and vomiting that prevent subjects from eating a meal on 3 or more occasions on 2 consecutive days in 1 or more subjects in a group.
- Diarrhea, defined as 7 or more episodes, rated as ≥ 5 on the Bristol Stool Chart, in 1 day for 2 consecutive days in 1 or more subjects in a group.
- Hematochezia and melena with visible blood that are considered to be caused by gastrointestinal bleeding in 1 or more subjects in a group.
- Clinically significant increases in liver function tests compared to baseline measurements, defined as AST, ALT, ALP, and/or γ -GTP $\geq 3 \times$ the upper limit of normal (ULN) and/or T-Bil $\geq 2 \times$ ULN (confirmed with repeat testing) in 2 or more subjects in a group.
- Maximum systemic exposure level of CCI [REDACTED] in individual subjects in the next group predicted to exceed a C_{max} of 1220 ng/mL and/or an AUC_{0-24h} of 3930 ng \cdot h/mL.

The dosing status of an individual subject may be unblinded to reviewers of the safety data if necessary for safety reasons or if pertinent to dose escalation decisions. The unblinded status will be kept to a minimum number of reviewers, based on pertinence to their role and relevant task. Further information on blinding can be found in [Section 5.4](#).

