^a Interim medical history.^b Female subjects only.^c Female subjects only. Serum pregnancy test at screening and urine pregnancy test at all other timepoints. A positive urine pregnancy test will be confirmed with a serum pregnancy test.^d Subjects will be fasted for at least 10 hours prior to dosing until 4 hours after dosing, after which time a meal will be provided.^e Collected in Group A5 only.^f Spot urine and faecal samples will be collected any time prior to dosing in the treatment period. 24-hour urine and faecal samples will be collected on 0 to 24, 24 to 48, and 48 to 72 hours postdose. Faecal samples will be collected, as far as possible.^g A continuous 12-lead ECG will be obtained from 2 hours predose to 24 hours postdose. The 15-minute predose posture restriction (supinely or semi-recumbently resting in an undisturbed environment) for continuous ECG monitoring will be performed in triplicate within the first 2 hours prior to dosing. Postdose 15-minute posture restrictions for continuous ECG monitoring will be performed at 0.5, 0.75, 1, 1.5, 2, 3, 4, 6, 8, 12 and 24 hours postdose. Additional posture restrictions may be performed if deemed necessary after the review of PK data at the dose escalation review meetings.^h From waking-up to before breakfast.ⁱ Subjects will be fasted at least 6 hours before collection.^j Faecal occult blood test will be performed once each during the following sampling periods: Screening, Day -1 to prior to dosing, 0 to 24, 24 to 48, and 48 to 72 hours postdose. On screening, faecal samples will be collected to confirm eligibility for enrollment. For the other sampling periods, faecal samples will be collected as far as possible.^k If the latest result during the treatment period is positive, faecal samples will be collected for faecal occult blood test at the follow-up visit (within -2 day), as far as possible.^l To be assessed when collecting faecal samples for faecal occult blood test during the treatment period.^m Subjects should be supine for at least 5 minutes before blood pressure and pulse rate measurements.ⁿ To be measured in triplicate at approximately 2-minute intervals.^o To be recorded after the subject has been supine and at rest for at least 5 minutes.

^p Full physical examination.

^q Symptom-directed physical examination.

^r Prior to discharge.

^s To be performed at approximately the same time as on Day 1.

^t The follow-up period may be extended depending on the observed $t_{1/2}$ of CCI

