Prior/concomitant medication monitoring																		
Body weight		X																X ^e
Haematology, clinical chemistry, coagulation, and urinalysis ^f		X														X ^e		X
Faecal occult blood test ^g			X													X		X ^h
Bristol Stool Chart ^h			X													X		X
Blood pressure, pulse rate, and respiratory rate ⁱ		X	X ^j						X		X		X		X	X ^e	X ^e	X
Oral body temperature		X	X													X ^e	X ^e	X
12-lead ECG for safety assessment ^k		X	X ^j			X		X		X		X		X	X ^e	X ^e	X	
Physical examination			X ^l														X ^{m,n}	X ^l
Abdominal examination		X								X					X ^o	X ^o	X ^o	

^a Interim medical history.^b Subjects will be fasted for at least 10 hours prior to dosing until 4 hours after dosing, after which time a meal will be provided.^c Spot urine and faecal samples will be collected any time prior to dosing in Treatment Period 1. 24-hour urine and faecal samples will be collected on 0 to 24, 24 to 48, and 48 to 72 hours postdose. Faecal samples will be collected, as far as possible.^d A continuous 12-lead ECG will be obtained from 2 hours predose to 24 hours postdose. The 15-minute predose posture restriction (supinely or semi-recumbently resting in an undisturbed environment) for continuous ECG monitoring will be performed in triplicate within the first 2 hours prior to dosing. Postdose 15-minute posture restrictions for continuous ECG monitoring will be performed at 0.5, 0.75, 1, 1.5, 2, 3, 4, 6, 8, 12 and 24 hours postdose. Additional posture restrictions may be performed if deemed necessary after the review of PK data at the dose escalation review meetings.^e From waking-up to before breakfast.^f Subjects will be fasted for at least 6 hours before collection.

^g Faecal occult blood test will be performed once each during the following sampling periods: Screening, Day -1 to prior to dosing, 0 to 24, 24 to 48, and 48 to 72 hours postdose in Treatment Period 1, and Day -1 to dosing, 0 to 24, 24 to 48, and 48 to 72 hours postdose in Treatment Period 2. On screening in Treatment Period 1, faecal samples will be collected to confirm eligibility for enrollment. For the other sampling periods, faecal samples will be collected as far as possible.

^h To be assessed when collecting faecal samples for faecal occult blood test in treatment periods.

ⁱ Subjects should be supine for at least 5 minutes before blood pressure and pulse rate measurements.

^j To be measured in triplicate at approximately 2-minute intervals.

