^a Interim medical history.^b Subjects will receive the IMP once daily at the same time as Day 1 in the fasted state (at least 10 hours).^c Subjects will be fasted until 4 hours after dosing, after which time a meal will be provided.^d Collected in Group B1 only.^e Spot urine sample will be collected any time prior to dosing. 24-hour urine samples will be collected on 0 to 24 hours postdose on Day 14.^f Subjects will be fasted at least 6 hours before collection.

^g Faecal occult blood test will be performed once each during the following sampling periods: Screening, Day -1 to prior to dosing, 0 to 24, 24 to 96, 96 to 168, 168 to 240 hours postdose on Day 1, 240 hours postdose on Day 1 to 0 hours on Day 14, and 0 to 72 hours postdose on Day 14. On screening, faecal samples will be collected to confirm eligibility for enrollment. For the other sampling periods, faecal samples will be collected as far as possible.

^h To be assessed when collecting faecal samples for faecal occult blood test in the treatment period.

ⁱ Subjects should be supine for at least 5 minutes before blood pressure and pulse rate measurements.

^j To be measured in triplicate at approximately 2-minute intervals.

^k To be recorded after the subject has been supine and at rest for at least 5 minutes.

^l Full physical examination.

^m Symptom-directed physical examination.

ⁿ Immediately before dosing.

^o From waking-up to before dosing.

^p To be performed at approximately the same time as on Day 1.

^q From waking-up to before breakfast.

^r If the latest result during the treatment period is positive, faecal samples will be collected for faecal occult blood test at the follow-up visit (within -2 day), as far as possible.

^s Prior to discharge.

^t The follow-up period may be extended depending on the observed $t_{1/2}$ of **CCI**

Table 12: Schedule of Assessments-Part C (DDI) [Screening to Day4]

Day	Screening	Treatment Period 1																
		-28 to -2	-1	1	2	3	4	6	8	12	24	36	48	72				
Time Postdose (h)		Pre	0	0.25	0.5	0.75	1	1.5	2	3	4	6	8	12	24	36	48	72
Informed consent	X																	
Inclusion/exclusion criteria	X	X																
Demographic data	X																	
Medical history	X	X ^a																
Urinary drug and cotinine screen	X	X																
Alcohol breath test	X	X																
Serology	X																	
Height	X																	
KRP-A218 and itraconazole administration^r																		
KRP-A218			X ^b															

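### The one-subject diarrhoea stopping count is not supported by the stool ratings the protocol requires, and SAP 8.1.4 leaves unscheduled ratings out of the Bristol summary tables

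*Protocol*

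**What the plan says.** **Stopping rule.** One of the criteria in Protocol 3.7 opens "Diarrhea, defined as 7 or more episodes", requires each episode to be rated 5 or higher, and continues "on the Bristol Stool Chart, in 1 day for 2 consecutive days in 1 or more subjects in a group". A different criterion in the same section covers clinically relevant signs of a similar nature in 2 or more subjects. It rests on the Investigator's opinion, names diarrhoea among the signs, and needs no count. Under that criterion "the Investigator (or designee) should carefully monitor signs or symptoms below".

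**Ratings.** Protocol 7.3.3 says: "The form of faeces will be assessed by clinical staff using the Bristol Stool Chart when collecting faecal samples for faecal occult blood test". It then allows more: "The form of faeces may also be assessed at other times if judged to be clinically appropriate". Appendix 6 ties the rating to the same sample, for example in Table 9 footnote l: "To be assessed when collecting faecal samples for faecal occult blood test during the treatment period". The frequency is in the occult-blood footnotes (Table 9 footnote j, Table 10 footnote g, Table 11 footnote g): "Faecal occult blood test will be performed once each during the following sampling periods". Postdose windows in Part A are 24 hours long, in both periods for Group A2a, whose list ends "24 to 48, and 48 to 72 hours postdose in Treatment Period 2". In Part B most are 72 hours long. Postdose samples are best effort (Protocol 7.3.2 and the footnotes).

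**Adverse event records.** Protocol 7.3.1 has residents observed and questioned at least daily. It requires the nature, onset, duration, severity and relationship of each event, but no stool count or Bristol type.

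**SAP.** For Bristol data, SAP 8.1.4 treats any value beyond the original as unscheduled and removes it from all calculations. Its exceptions are the baseline derivation and the 12-lead ECG outlier analysis. SAP 8.1 says that calculations include summary statistics. SAP 8.7.5 plans by-treatment and by-timepoint Bristol tables and does not mention unscheduled ratings.

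**The concern.** A rule that turns on a number needs a record that yields the number. Here the rule counts rated stools per day, while the schedule asks for about one rating a day in Part A and fewer in Part B. Protocol 3.7 does not say that the scheduled ratings are its source, but no passage names another.

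One subject decides this criterion, so a doubtful count on either day matters. Protocol 3.5 gives gastrointestinal toxicity in dogs as the reason for lower escalation increments. Loose stools are among the blinded adverse events in Protocol 1.3. That section also says all events were transient and mild or moderate, and 3.5 reports no gastrointestinal findings of concern at 1 to 6 mg. When this protocol version was written, the 12 mg group, the group of up to 24 mg and Part B were still ahead.

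The SAP issue is separate. The Bristol chart is a listed primary safety endpoint for Parts A and B (Protocol 2.2.1, SAP 3.1). The extra ratings that 7.3.3 allows are the ones most likely to be made because a stool looked abnormal, and those are the ratings that SAP 8.1.4 removes from the tables.

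**Working it through.** The plan gives no figure of its own here, so the check counts required ratings against the rule.

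**1. What the rule needs.** 7 episodes × 2 days = 14 rated episodes at least (Protocol 3.7).

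**2. Postdose windows, one required rating in each** (hours after first dose, Appendix 6 footnotes).
- Part A, per period: 0–24, 24–48, 48–72.
- Part B: 0–24, 24–96, 96–168, 168–240, 240–312, 312–384. The Day 14 dose falls at 13 × 24 = 312 h, and its 72 h window ends at 312 + 72 = 384 h.

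The average is 3/3 = 1 rating a day in Part A and 6/16 = 0.375 a day in Part B.

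**3. Required ratings in a 48 h span, if every sample is obtained.** The rating can fall anywhere in its window. The minimum is therefore the number of windows wholly inside the span, and the maximum is the number that overlap it.

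| Part | Example span (h) | Wholly inside | Overlapping |
|---|---|---|---|
| A | 0–48 | 2 | 2 |
| A | 12–60 | 1 | 3 |
| B | 0–48 | 1 | 2 |
| B | 24–72 | 0 | 1 |
| B | 72–120 | 0 | 2 |

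Over all postdose spans the range is 1 to 3 in Part A and 0 to 2 in Part B. Part B has 16 postdose days, hence 15 dose-aligned two-day spans. Only Days 1–2 contain a whole window, because a 72 h window cannot fit in 48 h. So 14 of the 15 may contain no required rating.

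**4. Shortfall.** At least 14 − 3 = 11 ratings in Part A and 14 − 2 = 12 in Part B must come from elsewhere.

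**5. Where else they could come from.**
- Extra ratings under 7.3.3 are discretionary.
- Adverse event records need not hold a count or type. Severity in Appendix 1 is graded by interference with daily activities and need for intervention, which does not convert to a count.
- 24-hour faecal collection (Protocol 7.2.1) covers Groups A2a (Period 1 only) and A5: 8 + 8 = 16 of 48 planned Part A subjects. It covers 0 of 40 in Part B, where B1 collects urine only. No Bristol rating is attached to it.
- Part B has an abdominal examination on each of Days 2 to 13, but this does not count stools.

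**6. SAP.** SAP 8.1.4 is a general rule with a closed list of exceptions, 8.1 extends it to summary statistics, and 8.7.5 claims no exception. Read together, unscheduled Bristol ratings appear in listings and not in summary tables. SAP 8.7.4 shows the SAP making an exception where extremes matter: its QTcF outlier analysis includes repeat and unscheduled values.

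**The case against.** The strongest reply is that escalation is well controlled without a complete stool log. Seven loose stools in a day in a resident subject is a plain case for the extra ratings that 7.3.3 allows, and daily questioning would probably bring it out. The Investigator-judged criterion in 3.7 can stop escalation for diarrhoea in 2 or more subjects without a count. Under 3.6, escalation needs a satisfactory safety review and the Investigator prevails in a disagreement, so a subject uncertain between 6 and 7 episodes can still halt escalation. All of this stands. A reader might infer that the stopping rule is unworkable. The documents do not support that, because the rule is event-driven and these routes remain open.

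The eCRF and its completion instructions are not among the documents and might contain a count field. That also stands. The finding is that the protocol does not require such a record, not that none exists.

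On the SAP, a reader might infer that 8.1.4 and 8.7.5 contradict each other, since 8.7.5 speaks of all Bristol data. The text does not bear this out. The SAP uses the same stock wording for phospholipid-C in 8.6.2, so 8.1.4 governs. Diarrhoea reported as a treatment-emergent event would also be tabulated by preferred term under SAP 8.7.1, so the signal need not vanish from the summaries.

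What survives is narrower. The no-count criterion needs a second subject and a judgement, whereas the diarrhoea criterion was written for one subject and a number. A preferred-term table does not show stool form.

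**Conclusion.** Both points hold in limited form and deserve a cheap correction.

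1. Required ratings cannot supply the 3.7 count, falling short of 14 by at least 11 in Part A and 12 in Part B. The criterion can still be applied, but on data that the protocol leaves to discretion. The counts assume every scheduled sample is obtained, so missed samples would widen the gap. They do not depend on whether a day means a dosing day or a calendar day, since every 48 h span was considered.

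2. Applied as written, the SAP omits unscheduled ratings from the tables of a primary safety endpoint for Parts A and B. This affects reporting only; listings and stopping decisions are unchanged. The TFL shells are not in the documents and might already deal with it.

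Nothing here bears on whether the diarrhoea threshold is clinically right.

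**What to change.** **Protocol.** Reconcile 3.7, 7.3.3 and the Bristol footnotes in Appendix 6 (Table 9 footnote l, Table 10 footnote h, Table 11 footnote h). The stool count and Bristol type used for the 3.7 criterion should be captured in a named source record during residence in Parts A and B, and included in the interim safety report described in 3.6. The threshold, and any clinical trigger for extra ratings, stay with the sponsor and investigator.

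**SAP 8.7.5.** Add a by-treatment summary of the maximum postdose Bristol type per subject, including unscheduled ratings, as a stated exception to 8.1.4 on the model of the QTcF outlier analysis in 8.7.4.

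**Cost.** A short protocol and eCRF edit, some staff recording time during residence that is already planned (to Day 4 of each period in Part A, to Day 17 in Part B), and one extra table. No added samples or visits.

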7.3.4. Vital Signs

Supine blood pressure, supine pulse rate, respiratory rate, and oral body temperature will be assessed at the times indicated in the Schedule of Assessments in [Appendix 6](#). Vital signs may also be performed at other times if judged to be clinically appropriate or if the ongoing review of the data suggests a more detailed assessment of vital signs is required.

For Day 1 predose in each treatment period in Parts A to C and Day 11 predose in Part C, blood pressure, pulse rate, and respiratory rate will be measured in triplicate at approximately 2-minute intervals. The median value will be used as the baseline value in the data analysis. All subsequent measurements will be performed singly and repeated once if outside the relevant clinical reference ranges. Oral body temperature will be measured singly.

Subjects should be supine for at least 5 minutes before blood pressure and pulse rate measurements.

7.3.5. 12-lead Electrocardiogram

Resting 12-lead ECGs will be recorded after the subject has been supine and at rest for at least 5 minutes at the times indicated in the Schedule of Assessments in [Appendix 6](#). Single 12-lead ECGs will be repeated once if either of the following criteria apply:

- QTcF value >500 msec
- QTcF change from the baseline (predose) is >60 msec.

Additional 12 lead ECGs may be performed at other times if judged to be clinically appropriate or if the ongoing review of the data suggests a more detailed assessment of ECGs is required. The Investigator (or designee) will perform a clinical assessment of each 12 lead ECG.

Day 1 predose 12-lead ECGs in each treatment period in Parts A to C and Day 11 predose in Part C will be measured in triplicate at approximately 2-minute intervals. The mean value will be used as the baseline value in the data analysis. All subsequent measurements will be performed singly and repeated once if outside the relevant clinical reference ranges.

7.3.6. Physical Examination

A full physical examination or symptom-directed physical examination will be performed by Investigator (or designee) at the time points specified in the Schedule of Assessments in [Appendix 6](#).

7.3.7. Abdominal Examination

An abdominal examination will be performed in Parts A and B by Investigator (or designee) and will include inspection, auscultation, palpation and percussion of the abdomen. The abdominal examination will be performed at the times indicated in the Schedule of Assessments in [Appendix 6](#).

When the physical examination and the abdominal examination are scheduled at the same day, the abdominal examination may be performed as part of the physical examination.

7.3.8. Height, Body Weight, and BMI

Height and body weight (in underclothes and with shoes off) will be recorded at the times indicated in the Schedule of Assessments in [Appendix 6](#). The BMI is calculated using metric units with the formula provided below.

BMI should be derived as:

Metric: $BMI = \text{body weight (kg)} / \text{height (m)}^2$

8. SAMPLE SIZE AND DATA ANALYSIS

8.1. Determination of Sample Size

No formal statistical assessment, in terms of sample size, has been conducted as this is the first time KRP-A218 is being administered to humans. However, the number of subjects in Parts A, B, and C is common in early clinical pharmacology studies/DDI studies, and is considered sufficient to achieve the objectives of the study.

8.2. Analysis Populations

8.2.1. Pharmacokinetic Population

The PK population will include all subjects who received at least 1 dose of active study treatment (KRP-A218 or itraconazole) and have at least 1 quantifiable PK concentration. A subject may be excluded from the PK summary statistics and statistical analysis if the subject has an AE of vomiting that occurs at or before 2-times t_{max} .

8.2.2. Safety Population

The safety population will include all subjects who received at least 1 dose of study treatment (KRP-A218, placebo, or itraconazole).

8.3. Pharmacokinetic Analyses

Noncompartmental PK analysis will be performed on individual plasma concentration data, using commercial software such as Phoenix® WinNonlin®. Plasma concentrations and PK parameters of CCI [REDACTED], itraconazole, and hydroxy-itraconazole will be listed and summarised by treatment group using descriptive statistics. Individual and mean concentration-time profiles for CCI [REDACTED] and itraconazole and hydroxy-itraconazole for each treatment group will also be presented graphically.

Where data are available, dose proportionality of CCI [REDACTED] will be examined across dose groups. The PK parameters will be analysed for dose proportionality using a power model approach and/or analysis of variance (ANOVA) model, as appropriate. Where data are available, the effect of food at 1 dose level in Part A, and the interaction between KRP-A218 alone and co-administered with itraconazole in Part C will be investigated using mixed-model; the effect of sex at 1 dose level in Part A will be investigated using ANOVA.

Data handling procedures will be documented in the Statistical Analysis Plan.

